6.7. Intervention after the End of the Study

Participants receiving study treatment at the time of the final analysis may continue to receive study treatment until treatment is discontinued as indicated in Section 7.1. At the time of the interim analysis or at final analyses (refer to Section 9.5), the IDMC may make a recommendation regarding the continuation of study treatment based on the outcome; this decision will be communicated to Investigators whereby subsequent communication to participants may be required.

Participants who permanently discontinue study treatment will not receive any additional treatment from GSK. The investigator is responsible for ensuring that consideration has been given to the post-study care based on the participant's medical condition. Refer to SoA (Table 1) and Section 7.1 for details on the follow-up assessments required for participants who permanently discontinued study treatment. Refer to Section 6.5.2.1 on prohibited post-study therapies.

7. DISCONTINUATION OF STUDY INTERVENTION AND PARTICIPANT DISCONTINUATION/WITHDRAWAL

7.1. Discontinuation of Study Intervention

Participants will receive study treatment for the duration indicated in Section 6.1 as applicable, unless one of the following events occurs earlier:

- Disease progression
- Death
- Unacceptable toxicity (refer to Section 6.6 and subsections)
- Pregnancy (refer to Section 8.3.5 for details)

In addition, study treatment may be permanently discontinued for any of the following reasons:

- Deviation(s) from the protocol or non-compliance with study requirements
- Request of the participant or proxy (withdrawal of consent by participant or proxy)
- Discretion of the investigator
- Participant is lost to follow-up
- Closure or termination of the study

Participants who have disease progression by RECIST v1.1 may continue study treatment up to the protocol specified 35 cycles at the discretion of the Investigator to confirm progression as per iRECIST guidelines. Nevertheless, the consideration to continue study treatment should be balanced by clinical judgment as to whether the participant is clinically stable. Continuation on study treatment is contingent upon the following conditions:

- Absence of clinical signs or symptoms indicating clinically significant disease progression
- ECOG PS has not worsened, or worsening by no more than 1 point from baseline
- Absence of rapid disease progression or threat to vital organs or critical anatomical sites (e.g., CNS metastasis, respiratory failure due to tumor)

- compression, or spinal cord compression) requiring urgent alternative medical intervention.
- No significant, unacceptable, or irreversible toxicities related to study treatment.

All participants who permanently discontinue study treatment for any reason (except consent withdrawn) will have safety assessments at the time of discontinuation and during follow-up as specified in the SoA.

The primary reason study treatment was permanently discontinued must be documented in the participant's medical records and eCRF. If the participant voluntarily discontinues from treatment due to toxicity, 'adverse event (AE)' will be recorded as the primary reason for permanent discontinuation on the eCRF.

Once a participant has permanently discontinued from study treatment, the participant will not be allowed to be retreated. Refer to the SoA for assessments to be performed at the time study treatment is permanently discontinued and for evaluations that need to be completed.

All participants who permanently discontinue study treatment without disease progression will be followed for progression according to the protocol-defined on-treatment disease assessment schedule in the SoA until one or more of the following occur:

- a new anticancer therapy is initiated
- disease progression
- death

All participants who permanently discontinue study treatment for any reason, except withdrawal of consent (refer to Section 7.2) will be followed for survival every 12 weeks until death or until the last participant discontinues treatment and has had their last follow up for safety.

The every 12-week schedule (refer to Table 1 SoA for details of frequency of all assessments during follow-up period) should begin once study treatment has been permanently discontinued. If participants are unable or unwilling to attend clinic visits during follow-up, contact to assess survival, may be made via another form of communication (e.g., telephone, email, etc.).

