Fresh Tumor Biopsy*	X*											*Optional biopsy at: 
 Screening in those participants who provide archival tumor tissue (refer to Section 5.1 for archival tissue requirements) 	
Follow-up Assessments													
Survival												Q12W Participants will be contacted via telephone contact every 12 weeks until death or participant's withdrawal from further contact or until the last patient discontinues treatment and has had their last follow up for safety.	

Abbreviations: AE = Adverse Events; AESI = Adverse Events of Special Interest;; ECG = electrocardiogram; ECHO = echocardiogram; ECOG PS= Eastern Cooperative Oncology Group Performance Status; EOI= end of infusion; HPV = human papilloma virus; ICF = Informed Consent Form; MUGA = Multigated Acquisition Scan; Q3W = every 3 weeks; Q6W = every 6 weeks; Q12W = every 12 weeks; Q24W = every 24 weeks; SAE = Serious Adverse Events; TDV = Treatment Discontinuation visit; WOCBP = woman of childbearing potential

1. If administration of study treatment is delayed ≤7 days due to adverse events, assessments indicated to occur at the dosing visit can be scheduled to occur when dosing occurs. If administration of study treatment is delayed > 7 days due to adverse events, assessments indicated at the dosing visit are to be performed at the expected scheduled visit (±window) with the exception of the following: PK sample collection; immunogenicity sample collection, and the PRO assessments. If the dosing Week visit that is delayed > 7 days occurs at a visit when disease assessments are required, then PRO assessments are required to be administered to the participant.
2. Do not repeat tests that have already been performed within 3 days or scans within 6 weeks of the TDV. The assessments required at the study treatment discontinuation visit (permanent discontinuation) must be completed within 30 days from the date study treatment was discontinued and must occur prior to the start of subsequent anti-cancer therapy; the window for this visit is +10 days.
3. The follow-up visits will commence after decision to permanently discontinue study treatment for any reason is made including completion of 35 cycles

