7.2. Participant Discontinuation/Withdrawal from the Study

- A participant may withdraw from the study at any time at his/her own request or may be withdrawn at any time at the discretion of the investigator for safety, behavioral, compliance or administrative reasons. This is expected to be uncommon.
- At the time of discontinuing from the study, an early discontinuation visit should be conducted, as shown in the SoA. Refer to SoA (Table 1) for the assessments at the time of study discontinuation
- The participant will be permanently discontinued both from the study intervention and from the study at that time.
- If the participant withdraws consent for disclosure of future information, the sponsor may retain and continue to use any data collected before such a withdrawal of consent.
- If a participant withdraws from the study, he/she may request destruction of any samples taken and not tested, and the investigator must document this in the site study records.

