7.3. Lost to Follow Up

A participant will be considered lost to follow-up if he or she repeatedly fails to return for scheduled visits and is unable to be contacted by the study site.

The following actions must be taken if a participant fails to return to the clinic for a required study visit:

- The site must attempt to contact the participant and reschedule the missed visit as soon as possible and counsel the participant on the importance of maintaining the assigned visit schedule and ascertain whether or not the participant wishes to and/or should continue in the study.
- Before a participant is deemed lost to follow up, the investigator or designee must make every effort to regain contact with the participant (where possible, 3 telephone calls and, if necessary, a certified letter to the participant's last known mailing address or local equivalent methods). These contact attempts should be documented in the participant's medical record.
- Should the participant continue to be unreachable, he/she will be considered to have withdrawn from the study.

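### Protocol 7.1 merges a request to stop treatment with withdrawal of consent, and 7.2 takes investigator-withdrawn participants off study, so survival follow-up can end sooner than the Schedule of Activities and the OS estimand require

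*Protocol*

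**What the plan says.** **Participant's request.** Among the reasons for permanently stopping treatment, Protocol 7.1 lists "Request of the participant or proxy (withdrawal of consent by participant or proxy". On safety, 7.1 says that participants who stop "for any reason (except consent withdrawn) will have safety assessments at the time of discontinuation and during follow-up as specified in the SoA". On survival, it says that those who stop "for any reason, except withdrawal of consent (refer to Section 7.2) will be followed for survival every 12 weeks". The follow-up paragraph of Section 8 repeats the survival exemption. One group is handled separately: "If the participant voluntarily discontinues from treatment due to toxicity, 'adverse event (AE)' will be recorded as the primary reason".

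**Schedule of Activities (Section 1.3).** Telephone contact for survival runs every 12 weeks until death or the participant's "withdrawal from further contact or until the last patient discontinues treatment" and completes safety follow-up. Footnote 3 starts follow-up visits after treatment stops for any reason, with no consent exception.

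**Investigator's decision.** Section 7.1 lists investigator discretion and non-compliance as treatment stops, and neither is exempt from follow-up. Section 7.2 lets the investigator withdraw a participant for safety, behavioural, compliance or administrative reasons, provides for an early discontinuation visit, and states: "The participant will be permanently discontinued both from the study intervention and from the study at that time".

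**Analysis.** SAP Table 2 handles treatment discontinuation under treatment policy for OS. SAP 4.2.1 censors participants without a documented death at the last date known alive.

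**The concern.** A treatment-policy estimand for OS needs deaths counted after every treatment stop, whatever the reason. If the reason code for stopping infusions is the same as the code for withdrawing consent, a site can close survival follow-up on someone who would have accepted a telephone call every 12 weeks. If an investigator uses 7.2 rather than 7.1 for the same event, such as non-compliance, follow-up ends instead of continuing.

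Those who leave may be sicker than those who stay, in which case censoring them is informative. The abbreviated main report still gives the OS hazard ratio and log-rank p-value (SAP 1 and 4.2.2), while sensitivity and supplementary analyses are dropped (SAP 4.2.3 and 4.2.4). No planned analysis would show the effect of such censoring. Safety is also touched, because a final report will update key safety analyses after the last visit (SAP 4.5).

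**Working it through.** The plan gives no figure for this point, so the check is first textual and then illustrative.

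**1. Same participant, different rule**

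| Situation | Protocol 7.1 and Section 8 | Protocol 7.2 | Schedule of Activities |
|---|---|---|---|
| Wants to stop infusions, accepts calls | Only matching reason is glossed as consent withdrawal, which is exempt from safety and survival follow-up | Off study, if treated as withdrawal | Calls continue |
| Stops voluntarily for toxicity | Coded as AE, stays in follow-up | – | Calls continue |
| Investigator stops for non-compliance or by discretion | Treatment stop, followed for survival | If withdrawn: off treatment and off study | Calls continue |
| Refuses all further contact | Exempt | Off study | Calls end |

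The first and third rows conflict. Section 7.2 itself separates withdrawal of consent to future disclosure from withdrawal in general, so the protocol already recognises levels of withdrawal that 7.1 merges.

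**2. Safety windows.** Section 8.3.1 counts 30 days (AEs) and 90 days (AESIs and SAEs) from the last dose, without an exception for withdrawn participants. It also says investigators need not actively seek events in former participants. Someone taken off study under 7.2 within those windows fits both statements, and nothing says which prevails.

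**3. Loss of information (context).** Inputs from Protocol 9.2.1: 410 deaths, hazard ratio 0.72, one-sided alpha 0.0249, yearly drop-out 5%. Fixed-design power is Φ(√(410/4) × |ln 0.72| − 1.962) = Φ(3.326 − 1.962) = 91.4%. Simulating the boundaries in Table 13 gives 90.6%, the stated figure. With the Section 9.2.1 survival assumptions, 410 deaths arrive at about month 40. If yearly drop-out were 10%, about 392 deaths would have occurred by then, with fixed-design power 90.1%. Doubling drop-out costs about 1.3 points, so lost information is minor; what matters is whether those lost differ.

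**4. Illustration of informative loss.** Assumptions, apart from the median: control median OS 13 months (Protocol 9.2.1), so λ = ln 2/13 = 0.0533 per month; 18 months of follow-up; a fraction p of an arm leaves at month 3; leavers have m times the hazard of death throughout; no other difference between arms. The arm with more leavers is thereby assumed truly to do worse.

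For each arm, R(t) = (1−p)e^(−λt) + p·e^(−mλt) and E(t) = λ(1−p)e^(−λt) + mλp·e^(−mλt). The leaver terms are set to zero after month 3 under the rule. The large-sample Cox log hazard ratio β solves ∫₀¹⁸ [E₁(1−x) − E₀x] dt = 0, with x = R₁e^β/(R₁e^β + R₀).

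| Leaving, by arm | m | Full follow-up | Leavers censored at month 3 |
|---|---|---|---|
| 15% v 5% | 2 | 1.07 | 1.02 |
| 15% v 5% | 3 | 1.11 | 1.04 |
| 10% v 5% | 2 | 1.035 | 1.01 |
| 10% v 5% | 3 | 1.05 | 1.02 |
| 10% v 10% or 15% v 15% | 2 or 3 | 1.00 | 1.00 |

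Simulated trials under the same assumptions agree to within about 0.01 (for example 1.03 to 1.05 in the last column for 15% v 5%).

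**The case against.** The best defence is that 7.1 governs treatment and 7.2 governs the study. The survival exemption in 7.1 refers the reader to 7.2, so it can be read as covering only withdrawal from the study. Stops for toxicity are coded as AEs and stay in follow-up, and 7.1 allows telephone or email contact for those unwilling to attend. Section 7.2 expects withdrawal to be uncommon, and the OS design allows 5% yearly drop-out. Screening has stopped and no interim analyses will be run, so little OS inference remains.

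All of this narrows the point. It does not supply a reason code for someone who declines infusions but accepts calls, and the safety exemption in 7.1 carries no reference to 7.2.

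A reader might infer more than the text supports:

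- That such participants are certainly lost to OS. The cross-reference to 7.2 allows the milder reading; they can be dropped, not must be.
- That 7.2 ends the 30- and 90-day safety collection. No passage says so. Section 8.3.3 follows SAEs and AESIs until resolved, stabilised, explained or lost to follow-up, and 8.3.1 still requires later-learned related SAEs to be reported. The interaction is unstated.
- That 7.3, under which "Should the participant continue to be unreachable, he/she will be considered to have withdrawn from the study", discards data the Schedule would collect. The Schedule's contact is a telephone call, and 7.3 applies only after contact attempts have failed. It does not forbid a later vital-status check.
- That requests to stop rose after the April 2021 letter, or rose unequally. The documents do not say this. The trial is double-blind and the letter stopped investigational drug and placebo alike.

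**Conclusion.** The wording conflict is real in two places: the merged reason in 7.1 against the Schedule's stop rule, and investigator withdrawal in 7.2 against the corresponding treatment stops in 7.1. Both allow avoidable censoring of a primary endpoint whose estimand calls for continued follow-up.

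The number affected and their prognosis are not in the documents, so no bias can be asserted. Between-arm bias needs leaving to differ by arm in frequency, timing or the prognosis of those who leave, and the double-blind design gives no positive reason to expect that. In the assumed unequal cases, the rule hides roughly 0.02 to 0.06 of the hazard ratio in the arm with more leavers.

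This is an inexpensive improvement worth making, of limited consequence for OS after early termination and still relevant to the final safety update.

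**What to change.** - In 7.1 and the eCRF, replace the single reason by two: *participant asks to stop study treatment (remains in safety and survival follow-up)* and *participant withdraws from further contact*.
- In 7.1, 7.2 and Section 8, make the Schedule's rule, withdrawal from further contact, the only participant-initiated end to survival contact.
- In 7.2, state that investigator-initiated withdrawal is from treatment and visits only, and that the 8.3.1 AE, AESI and SAE windows and survival contact continue unless the participant withdraws from further contact. The investigator's freedom to withdraw a participant is unchanged.

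No change to 7.3 is needed for this point. The cost is wording in three sections, one extra eCRF code and a few more telephone calls on a schedule that already exists. Participants who refuse contact are fully respected.

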7.1.1. Liver Chemistry Stopping Criteria

Liver chemistry stopping, and increased monitoring criteria have been designed to assure participant safety and evaluate liver event etiology.

Discontinuation of study intervention for abnormal liver tests is required when:

- a participant meets one of the conditions outlined in Section 10.8 and Section 6.6.1 or

- when in the presence of abnormal liver chemistries not meeting protocol-specified stopping rules, the investigator believes study intervention discontinuation is in the best interest of the participant.

7.1.2. Rechallenge

7.1.2.1. Study Intervention Restart or Rechallenge after liver stopping criteria met

If participant meets liver chemistry stopping criteria do not restart/rechallenge participant with study intervention unless:

- GSK Medical Governance approval **is granted**
- Ethics and/or IRB approval is obtained, if required, and
- Separate consent for intervention restart/rechallenge is signed by the participant

Refer to Section 10.8 and Section 10.8.1 for details.

If GSK Medical Governance approval to restart/rechallenge participant with study intervention **is not granted**, then participant must permanently discontinue study intervention and may continue in the study for protocol-specified follow up assessments.

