6.6. Dose Modification

Distinct safety management guidelines, including dose modification algorithms, are provided in this section for:

- GSK3359609
- Pembrolizumab

Refer to chemotherapy prescribing information or standard practice guidelines for the management of chemotherapy-related AEs or potential safety-related issues; including resuming chemotherapy treatment and dose reductions following recovery of AE.

Please note: In instances where the investigator is directed to permanently discontinue study treatment, the instructions are mandatory as described in Section 7.1.

All AEs are to be graded according to NCI-CTCAE (version 5.0) [NCI, 2017]. All dose modifications and the reason(s) for the dose modification must be documented in the eCRF.

Refer to pembrolizumab prescribing information [KEYTRUDA, 2019] or IB [Merck, 2021] for additional information regarding the background and the management of other AEs or potential safety-related issues. The investigator may consult the GSK Medical Monitor on study treatment modifications (i.e., holds or discontinuation) or on the management of AEs.

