- For severe and life-threatening irAEs, IV corticosteroid should be initiated first followed by oral steroid. Other immunosuppressive treatment should be initiated if irAEs cannot be controlled by corticosteroids.

Immune-related AEs	Severity Grade or Condition (CTCAEv5.0)	Action Taken to ^a : GSK3359609/ Pembrolizumab	Management: Corticosteroid and/or Other Therapies	Monitoring and Follow-up
Respiratory				
Pneumonitis	Grade 2	Withhold	
 • Administer corticosteroids (initial dose of 1-2 mg/kg prednisone or equivalent) followed by taper • Add prophylactic antibiotics for opportunistic infections 	
 • Monitor participants for signs and symptoms of pneumonitis. • Evaluate participants with suspected pneumonitis with radiographic imaging and initiate corticosteroid treatment.
	Grade 3 or Grade 4, or recurrent Grade 2	Permanently discontinue		
Gastrointestinal				
Diarrhea / Colitis	Grade 2 or Grade 3	Withhold	
 • Administer corticosteroids (initial dose of 1-2 mg/kg prednisone or equivalent) followed by taper 	
 • Monitor participants for signs and symptoms of enterocolitis (i.e., diarrhea, abdominal pain, blood or mucus in stool with or without fever) and of bowel perforation (i.e., peritoneal signs and ileus). • Participants with ≥ Grade 2 diarrhea suspecting colitis should consider GI consultation and performing endoscopy to rule out colitis. • Participants with diarrhea/colitis should be advised to drink liberal quantities of clear
	Grade 4 or recurrent Grade 3	Permanently discontinue		

Immune-related AEs	Severity Grade or Condition (CTCAEv5.0)	Action Taken to ^a : GSK3359609/ Pembrolizumab	Management: Corticosteroid and/or Other Therapies	Monitoring and Follow-up
				fluids. If sufficient oral fluid intake is not feasible, fluid and electrolytes should be substituted via IV infusion.
Hepatobiliary				
AST / ALT elevation or increased bilirubin	Grade 2	Withhold	
 Administer corticosteroids (initial dose of 0.5-1 mg/kg prednisone or equivalent) followed by taper 	
 Monitor with liver function tests (consider weekly or more frequently until liver enzyme value returned to baseline or is stable).

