	Grade 3 or Grade 4	Permanently discontinue	
 Administer corticosteroids (initial dose of 1-2 mg/kg prednisone or equivalent) followed by taper 	
 Refer to Section 10.8 for liver safety required actions and follow-up assessments and study treatment guidelines.
Endocrine				
Type 1 diabetes mellitus (T1DM) or Hyperglycemia	New onset T1DM or Grade 3 or Grade 4 hyperglycemia associated with evidence of β -cell failure	Withhold ^b	
 Initiate insulin replacement therapy for participants with T1DM Administer anti-hyperglycemic in participants with hyperglycemia 	
 Monitor participants for hyperglycemia or other signs and symptoms of diabetes.
Hypophysitis	Grade 2	Withhold	
 Administer corticosteroids and initiate hormonal replacements as clinically indicated. 	
 Monitor for signs and symptoms of hypophysitis (including hypopituitarism and adrenal insufficiency).
	Grade 3 or Grade 4	Withhold or permanently discontinue ^b		
Hyperthyroidism	Grade 2	Continue	
 Treat with non-selective beta-blockers (e.g., propranolol) or thionamides as appropriate 	
 Monitor for signs and symptoms of thyroid disorders.
	Grade 3 or Grade 4	Withhold or Permanently discontinue ^b		
Hypothyroidism	Grade 2, Grade 3, or Grade 4	Continue	
 Initiate thyroid replacement hormones (e.g., 	
 Monitor for signs and symptoms of thyroid disorders

Immune-related AEs	Severity Grade or Condition (CTCAEv5.0)	Action Taken to ^a : GSK3359609/ Pembrolizumab	Management: Corticosteroid and/or Other Therapies	Monitoring and Follow-up
			levothyroxine or liothyronine) per standard of care	
Renal				
Nephritis: Grade according to increased creatinine or acute kidney injury	Grade 2	Withhold	
 Administer corticosteroids (prednisone 1-2 mg/kg or equivalent) followed by taper 	
 Monitor changes of renal function
	Grade 3 or Grade 4	Permanently discontinue		
Cardiovascular				
Myocarditis	Grade 2	Permanently discontinue	
 Based on severity of AE administer corticosteroids 	
 Ensure adequate evaluation to confirm etiology and/or exclude other causes.

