10.8.1. Study Intervention Rechallenge Guidelines

10.8.1.1. Rechallenge Following Liver Stopping Events that are Possibly Related to Study Treatment

Following drug-induced liver injury, **drug rechallenge is associated with a 13% mortality across all drugs in prospective studies** [Andrade, 2009]. Clinical outcomes vary by drug, with nearly 50% fatality with halothane readministered within one month of initial injury. However, some drugs seldom result in recurrent liver injury or fatality.

Risk factors for a fatal drug rechallenge outcome include:

- Hypersensitivity [Andrade, 2009] with initial liver injury (e.g. fever, rash, eosinophilia)
- Jaundice or bilirubin $> 2x$ ULN with initial liver injury (direct bilirubin $> 35\%$ of total)
- Participant currently exhibits severe liver injury defined by: ALT $\geq 3x$ ULN, bilirubin $\geq 2x$ ULN (direct bilirubin $> 35\%$ of total), or INR ≥ 1.5
- Serious adverse event or fatality has earlier been observed with drug rechallenges [Hunt, 2010; Papay, 2009]
- Evidence of drug-related preclinical liability (e.g. reactive metabolites; mitochondrial impairment [Hunt, 2010])

Rechallenge refers to resuming study treatment following drug induced liver injury (DILI). Because of the risks associated with rechallenge after DILI this should only be considered for a participant for whom there is compelling evidence of benefit from a critical or life-saving medicine, there is no alternative approved medicine available, and a benefit:risk assessment of rechallenge is considered to be favorable.

Approval by GSK for rechallenge with study treatment can be considered where:

- Investigator requests consideration of rechallenge with study treatment for a participant who is receiving compelling benefit with study treatment that exceeds risk, and no effective alternative therapy is available.
- Ethics Committee or Institutional Review Board approval for rechallenge with study treatment must be obtained, as required.
- If the rechallenge is approved by GSK Medical Governance in writing, the participant must be provided with a clear description of the possible benefits and risks of study treatment administration, including the possibility of recurrent, more severe liver injury or death.
- The participant must also provide signed informed consent specifically for the rechallenge with study treatment. Documentation of informed consent must be recorded in the study chart.

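### For Grade 3–4 immune-related liver events that also meet a Table 17 stopping criterion, the protocol both makes the stop permanent at once and leaves rechallenge open

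*Protocol*

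**What the plan says.** Two sets of instructions govern liver toxicity.

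**Dose-modification rules.** Table 6 (Protocol 6.6.1) has a hepatobiliary entry for "AST / ALT elevation or increased bilirubin". Grade 2 leads to withholding. Grade 3 or Grade 4 leads to "Permanently discontinue", with no footnote or exception. Section 6.6 adds: "In instances where the investigator is directed to permanently discontinue study treatment, the instructions are mandatory as described in Section 7.1". Section 7.1 adds: "Once a participant has permanently discontinued from study treatment, the participant will not be allowed to be retreated". The monitoring column of the hepatobiliary entry then says: "Refer to Section 10.8 for liver safety required actions and follow-up assessments and study treatment guidelines".

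**Liver stopping and rechallenge rules.** Section 7.1.1 requires discontinuation for abnormal liver tests when "a participant meets one of the conditions outlined in Section 10.8 and Section 6.6.1 or" when the investigator otherwise judges stopping to be best for the participant. Section 7.1.2.1 says: "If participant meets liver chemistry stopping criteria do not restart/rechallenge participant with study intervention unless" the sponsor's medical governance approves, ethics or IRB approval is obtained where needed, and the participant signs a separate consent. If governance approval is refused, discontinuation becomes permanent. Appendix 8 has a section titled "Rechallenge Following Liver Stopping Events that are Possibly Related to Study Treatment" (10.8.1.1). It defines rechallenge as resumption after drug-induced liver injury and sets further conditions on benefit, lack of alternatives and written approval. Table 17 forbids restart unless two things hold: the protocol permits it, and sponsor governance approves. For this it refers to 7.1.2.1.

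**The concern.** A treatment-related, immune-mediated liver event can satisfy both sets of rules. Under the first, the decision is closed as soon as the grade is assigned. Under the second, it stays open until the sponsor decides on a request. Neither an investigator nor an ethics committee can tell from the text whether such a request is admissible.

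What is at stake is mainly participant safety and consistent management. The rules still apply: feladilimab/placebo dosing has stopped, but the current Schedule of Activities continues pembrolizumab for up to 35 cycles and chemotherapy for up to 6. A secondary effect is on the safety data. Exposure, adverse events leading to discontinuation, and liver stopping events (SAP 4.5.1, 4.5.3, 4.5.5.1) could reflect different handling of similar cases.

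**Working it through.** No arithmetic applies, and the plan gives no figure to reproduce. The check asks whether one participant can fall under both rules, and whether any text ranks them.

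**Step 1. Do both rules cover the same drugs?** Yes. Footnote a of Table 6 extends its actions to placebo and chemotherapy. The footnote to the Appendix 8 algorithm extends that guideline to every study drug.

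**Step 2. Do both rules cover the same kind of event?** In part. Table 6 covers immune-related events, which 6.6.1 describes as associated with immunotherapy. Section 10.8.1.1 covers liver stopping events possibly related to study treatment. An immune-related hepatic event attributed to study treatment is within both.

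**Step 3. Can one laboratory result meet both thresholds?** Yes. The ALT-absolute criterion in Table 17 is ALT at or above 8×ULN and at or above 2× baseline, with no upper limit. The Grade 3 or 4 entry in Table 6 has no ceiling either. The documents do not give the CTCAE cut-points. As long as grade rises with ALT and Grade 4 is open-ended upwards, a high enough ALT meets both, wherever the cut-points lie.

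**Step 4. What does each rule then require?**

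| | Table 6 with 6.6 and 7.1 | 7.1.2.1 with 10.8.1.1 |
|---|---|---|
| When the stop becomes permanent | At once, on Grade 3 or 4 | If sponsor approval is refused, or if stopping criteria are met again after rechallenge |
| Resumption | Not allowed | Possible with governance approval, ethics/IRB approval where needed, and separate consent |

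A stop cannot be both final at once and provisional pending approval.

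**Step 5. Does Table 6 contain a way back?** Not for this entry. Its general instructions on resuming concern treatment that was withheld. Footnote b, which gives discretion and allows resumption, is attached to endocrine entries and not to the hepatobiliary one.

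**Step 6. Does any text rank the two rules?** None was found. Table 6 sends the reader to 10.8, and 7.1.1 cites 10.8 and 6.6.1 together. Table 17's condition that the protocol must permit restart leads to 7.1.2.1, which has no exclusion for events that Table 6 makes permanent. Figure 2, the liver algorithm, is not shown in the text available here, so this step rests on the wording alone.

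**The case against.** The strongest reply is that Table 17 already resolves the matter. It sets two separate conditions, permission under the protocol and sponsor approval, and directs permanent discontinuation if either fails. An event for which Table 6 orders a mandatory permanent stop could be said to fail the first condition. That reading is reasonable, but the text does not secure it: the line refers to 7.1.2.1, which leaves such events in. The opposite argument, that the liver pathway is the more specific provision and overrides Table 6, is no better supported, since the Table 6 entry is itself liver-specific and declared mandatory.

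A second reply is that rechallenge is tightly controlled, so no site could restart treatment simply by reading one section. This stands, and it limits how far practice could vary between sites. It does not tell anyone whether a request may be made.

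Three stronger readings are tempting and are not supported:

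- **That every liver stopping event meets opposite rules.** Events outside the Table 6 Grade 3–4 hepatic entry, and events not related to treatment (10.8.1.2), follow the Appendix 8 pathway without this conflict.
- **That the 7.1 bar on retreatment by itself contradicts 7.1.2.1.** It does not, because 7.1.2.1 places rechallenge before discontinuation becomes permanent. The clash arises because Table 6 makes the stop permanent immediately.
- **That the 13% rechallenge mortality in 10.8.1.1 measures the effect.** It is a literature value across all drugs, quoted as a reason for caution. It says nothing about how often this inconsistency would matter, or about this regimen.

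**Conclusion.** The protocol contains a genuine but narrow conflict. It applies to Grade 3–4 immune-related AST/ALT or bilirubin elevation that also meets a Table 17 stopping criterion and is possibly related to study treatment. For such a participant the two sets of instructions cannot both be followed, and the wording does not say which prevails.

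Its size cannot be stated, because the number of participants affected is not in the documents. The pool is limited to those still receiving pembrolizumab, with or without chemotherapy. The conclusion assumes that CTCAE grading of ALT is open-ended at the top and that the missing Figure 2 contains no ranking of the rules. It should be corrected because it bears on safety. It does not touch the efficacy hypotheses or the error control.

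**What to change.** Reconcile Table 6 (hepatobiliary entry, Grade 3 or 4), 6.6, 7.1, 7.1.2.1, Table 17 and 10.8.1 in four steps:

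1. State explicitly whether the rechallenge pathway is available for events for which Table 6 directs permanent discontinuation.
2. Put that statement in 7.1.2.1, since the other sections lead there, and repeat it as a footnote to the Table 6 entry.
3. Make Table 17's condition of protocol permission refer to that statement.
4. Word the retreatment sentence in 7.1 to match, and check Figure 2 against it.

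Which rule should apply is a clinical decision for the sponsor, and this review proposes neither. The cost is wording in an amendment or a clarification letter. No change to data collection or analysis is needed.
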